15.6.3 Secondary Objective: Tumor Antigens (pp65) After Booster Vaccination

Objective: To assess whether pp65-specific polyfunctional T cells increase after booster vaccination with P30-linked pp65 peptide

Analysis Set: Analyses will be conducted in 2 different datasets:

- i. All CMV seropositive patients treated at the CMV seropositive MTD who have day 84 and day 140 PBMCs collected, and
- ii. All CMV seronegative patients treated at the CMV seronegative MTD who have day 84 and day 140 PBMCs collected.

Outcome: For analyses associated with pp65 among CMV seropositive patients treated at the CMV seropositive MTD, the outcome is mean fold increase in pp65-specific T cells between day 84 and 140.

For analyses associated with pp65 among CMV seronegative patients treated at the CMV seronegative MTD, the outcome is percent of patients who develop pp65-specific polyfunctional T cells due to vaccination between day 84 and day 140.

Hypothesis: Booster vaccination with pp65-linked P30 will increase the number of pp65-specific CD8⁺ polyfunctional T cells on day 140 over day 84.

Analysis Plan: Among CMV seropositive patients treated at the CMV seropositive MTD, a one-sample t-test will assess the mean fold increase in pp65-specific T cells between day 84 and day 140.

Among CMV seronegative patients treated at the CMV seronegative MTD, the proportion of patients with a pp65-specific response between day 84 and day 140 will be estimated.

Analyses described will be conducted among patients who complete all of the first 5 vaccines. Analyses will be conducted separately for patients who receive vaccine #6 and #7 without completion of the first 5 vaccines.

15.6.4 Secondary Objective: Tumor Associated Antigens (EphA2 and survivin) After Booster Vaccination

Objective: To assess whether EphA2- and survivin-specific polyfunctional T cells increase after booster vaccination with P30-linked EphA2 and survivin peptides

Analysis Set: All patients treated at the MTD who have day 84 and day 140 PBMCs collected

Outcome: For analyses associated with EphA2 and survivin, the outcome is mean fold increase in EphA2- and survivin-specific T cells between day 84 and day 140

Hypothesis: Booster vaccination with EphA2 and survivin linked to P30 will increase the number of EphA2- and survivin-specific CD8⁺ polyfunctional T cells on day 140 over day 84.

Analysis Plan: A one-sample t-test will assess whether there is a significant mean fold increase in EphA2- and survivin-specific T cells between day 84 and day 140.

If the MTD among CMV seropositive patients is different from the MTD for CMV seronegative patients, then these analyses may be conducted separately within the two strata.

15.6.5 Secondary Objective: Survival and PFS

Objective: Describe the survival and PFS of patients who received a P30-EPS vaccine

Analysis Set: All patients who initiate P30-EPS vaccine treatment

Outcome: Survival time is the time between first P30-EPS vaccination and death, or last patient follow-up if the patient remains alive. PFS is defined as the time between first P30-EPS vaccination and initial failure (disease progression or death). PFS is censored at the last follow-up, if the patient remains alive without disease progression.

Hypothesis: Descriptive

Analysis Plan: The Kaplan-Meier estimator will describe the survival of patients treated on this protocol. Median survival will be estimated with confidence intervals, along with estimates for 12, 24, and 36-month survival.

Additionally, the Cox proportional hazards model may explore the impact of CMV status on survival and PFS outcome.

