interfere with the desired immune response to the investigational vaccine. It is strongly recommended that patients should not be receiving bevacizumab prior to vaccine 1. If patients are started on the radiation necrosis dose of bevacizumab for the purpose of managing intracranial inflammatory responses, the vaccine/return to clinic schedule for this study will not change. The bevacizumab schedule will be independent of the vaccine schedule, since it will be provided clinically, and will be managed by the oncology office administering this medication.

Baseline bloodwork for subclinical manifestations of autoimmunity as outlined in Section 12.6.5 will be taken on all subjects prior to vaccine #1 and then only repeated if clinically indicated. Bloodwork for immunological monitoring will be taken at baseline, at vaccinations 1, 5, 6, and 7 before the vaccine is given (days 1, 22, 84, and 140). The total amount of blood required for this purpose will be about 90 mL. Peripheral blood for immunologic immune monitoring will be delivered to the dedicated lab for processing. Further details are available in the ETAPA correlative laboratory manual.

Magnetic resonance (MR) images will be obtained after completing XRT/TMZ for baseline measurements and to assess progression. Patients will then be imaged at visits prior to receiving vaccines #5, #6, and #7. The RANO 2.0 criteria will be used for assessment of response and pseudoprogression following treatment [62].

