9.3 Rationale for Correlative Studies

Immunological assessments will be used to measure the endpoints of the study. The peripheral blood samples collected in this study are used for assessing the impact of P30 linked EphA2, CMV pp65, and survivin peptides (detailed in Section 12.6.5 Immunological Evaluations). The exploratory biomarkers outlined in Section 15.7.2 will be assessed in archival tumor tissue, as well as any additional tumor tissue that may be obtained from future surgeries from patients throughout the course of the study. DNA and RNA sequencing will be performed on the archival tissue to describe any association between clinical findings including survival and PFS, and specific signatures that have been reported in the literature to correlate with clinical outcomes in immunotherapy trials in GBM. We expect patients with better clinical outcomes such as longer OS and PFS compared with similar historical controls, to have distinct immunological characteristics that we may define from the exploratory analyses. The sample size in this trial will not have statistical power to draw meaningful conclusions about these features, but the findings are likely to be hypothesis generating.

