12.5.2 Follow-up Requirements for Early Withdrawal

All patients who receive a vaccine will be followed for PFS and survival (please see Section 15.6.5) until death or loss to follow-up. Subjects will also be assessed and followed for SAE monitoring/safety analysis for 30 days following the last vaccine injection.

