12.6.3 Radiologic Evaluations

Patients with newly diagnosed GBM will be imaged by MRI as per standard of care for eligibility and baseline measurements, and to assess progression prior to vaccine therapy; although the purpose of this study is not to detect tumor responses, any evidence of tumor response will be determined using the Duke PRTBTC SOP. Progression will be defined in accordance with RANO 2.0 criteria, or “≥25% increase in the sum of bi-perpendicular diameters of enhancing disease on two separate scans at least 4 weeks apart; or new lesions; or substantial worsened T2/FLAIR; or substantial clinical decline” [62].

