assess the optimal threshold for differentiating short versus long-term survival; the sensitivity and specificity of each biomarker will be compared. A Cox proportional hazards model will assess the joint effect of all biomarkers on survival to discern if an integrated biomarker approach is more effective in predicting survival outcome. Correction for multiple comparisons using gene expression analyses will use the False Discovery Rate.

15.7.3 Exploratory Objective: Assess resected tumor for expression of the vaccine targets (i.e. EphA2, pp65, and survivin)

Objective: Assess resected tumor for expression of the vaccine targets (i.e. EphA2, pp65, and survivin)

Analysis Set: Any available tumor tissue from patients on-study prior to and/or after P30-EPS vaccination

Outcome: Association between the vaccine targets (EphA2, pp65, and survivin) and clinical outcomes

Hypothesis: Expression of vaccine targets will associate with survival and other exploratory endpoints

Analysis Plan: RNA-seq analysis of tumor tissue will be used to determine expression levels of vaccine targets, in transcripts per million and expression will be linked with survival and PFS after P30-EPS vaccination. For patients with available post-P30-EPS vaccination tumor tissue, pre- vs post P30-EPS vaccine expression levels of antigens will be determined to test if antigen escape/immunoediting of vaccine antigens occurs as well as if T cell inflammation post- P30-EPS vaccination associates with vaccine antigen expression.

15.7.4 Exploratory Objective: Assess changes in the tumor immune microenvironment, mutational heterogeneity/clonality, neoantigen depletion, and their association with survival.

Objective: Assess changes in the tumor immune microenvironment, mutational heterogeneity/clonality, neoantigen depletion, and their association with survival.

Analysis Set: Any available tumor tissue from patients on-study prior to and/or after P30-EPS vaccination

Outcome: Since productive immune surveillance is associated with immunoediting (e.g., depletion of immunogenic glioma cell clones), the associations between putative neoantigen depletion, mutational heterogeneity, gene expression signatures of T cell inflammation, and survival will be tested.

Hypothesis: Neoantigen depletion, reduced mutational heterogeneity, and increased T cell inflammation will be associated with improved survival in GBM patients treated with the P30-EPS vaccine.

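### PFS is censored at last follow-up rather than at the last disease assessment, so time without a scan after Day 84 or Day 140 can count as progression-free

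*Combined protocol and SAP*

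**What the plan says.** Section 15.6.5 times both outcomes from first vaccination. For survival: "Survival time is the time between first P30-EPS vaccination and death, or last patient follow-up if the patient remains alive". For PFS the event is progression or death, and "PFS is censored at the last follow-up, if the patient remains alive without disease progression". Neither that section nor any other defines a disease-assessment date for PFS.

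On imaging, Section 9.1 gives a baseline scan after chemoradiation and then: "Patients will then be imaged at visits prior to receiving vaccines #5, #6, and #7". Table 3 and Section 12.2 place those scans at Days 22, 84 and 140. Sections 12.3 and 12.5.2 add no later MRI. Section 12.5.2 nevertheless states: "All patients who receive a vaccine will be followed for PFS and survival", until death or loss to follow-up.

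Section 12.6.3 gives four routes to progression. Three need imaging: growth of enhancing disease, new lesions and worse T2/FLAIR. The fourth is substantial clinical decline.

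Median PFS is a listed endpoint (Section 8), and Section 5.5 plans Kaplan-Meier PFS within each CMV stratum. Section 15.6.5 allows a Cox model of PFS by CMV status. Under the vaccine-target objective in Section 15.7.3, "expression will be linked with survival and PFS after P30-EPS vaccination".

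**The concern.** The two endpoints need different evidence. A telephone call shows that a patient is alive. It does not show that the tumor has not grown. If both are censored at the last contact, a patient whose tumor was last assessed at Day 84 stays in the PFS risk set, without an event, for as long as someone can confirm survival.

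The error has one direction. An undetected progression becomes either a later death event or censoring at a late date, and both lengthen apparent PFS. The trial has no control arm in which the same error would cancel, and Section 9.3 looks toward an outside comparison: "We expect patients with better clinical outcomes such as longer OS and PFS compared with similar historical controls".

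The strata are small. Section 15.9 anticipates 24 patients at the MTD, one-third of them seropositive (8), and at most 6 more seropositive patients at other doses. On those numbers one wrongly extended patient is at least 1/14 = 7% of the seropositive curve.

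**Working it through.** The plan gives no expected PFS, event count or precision, so there is no figure to reproduce. The check has three steps.

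**1. One patient under each rule.** Suppose a patient stops after the Day 84 MRI, has no documented progression, and is known to be alive at 24 months (24 × 30.4375 ≈ 730 days).
- As written: censored at Day 730.
- By last MRI: censored at Day 84.
- Difference: 730 − 84 = 646 days credited as progression-free without a scan.

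**2. Effect on median PFS.** This is a simulation, and every input below is an assumption except the Day 22, 84 and 140 scans and the maximum of 36 patients.
- 36 patients, 2,000 trials per setting.
- Exponential time to progression, median 4, 6 or 8 months; post-progression survival median 9 months.
- Accrual over 30 months plus 6 months of follow-up.
- Scans at Days 22, 84 and 140, then every 56 days.
- A share q of patients has no MRI after Day 84 or Day 140 (half each) and no later progression documented, but is followed for survival.
- Deaths count as events throughout.

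The first difference is the total overstatement (rule as written minus full imaging). The second is what last-MRI censoring removes (rule as written minus last-MRI rule). The remainder is the first minus the second. All are average shifts in median PFS, in days.

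| True median | q | Total | Removed | Remainder |
|---|---|---|---|---|
| 4 months | 10% | 2 | 0 | 2 |
| 4 months | 20% | 4 | 1 | 3 |
| 4 months | 30% | 8 | 1 | 7 |
| 6 months | 10% | 8 | 2 | 6 |
| 6 months | 20% | 17 | 6 | 11 |
| 6 months | 30% | 28 | 13 | 15 |
| 8 months | 10% | 15 | 7 | 8 |
| 8 months | 20% | 31 | 20 | 11 |
| 8 months | 30% | 52 | 35 | 17 |

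The total is 2-52 days, of which the rule change removes 0-35. The remainder arises because unscanned patients contribute only deaths as later events, and no censoring rule recovers a progression that nobody recorded. The median was unchanged from full imaging in 36-95% of simulated trials, depending on the setting.

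**3. Outer bounds.** A separate simulation used scans at Days 22, 84 and 140 only, follow-up of 12-36 months and post-progression survival medians of 6 or 10 months. It varied the share of progressions after Day 140 that are detected when they occur.

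| True median | None detected | Half detected | All detected |
|---|---|---|---|
| 6 months | 10.4-12.4 months | 7.2-7.4 months | no inflation |
| 8 months | 14.5-17.3 months | 10.4-11.2 months | no inflation |

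With a true median of 4 months the reading is 4.6 months whatever is detected later. That is the Day 140 scan (140 / 30.4375 = 4.6), so it reflects the scan grid and not the censoring rule.

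**The case against.** The best case for leaving the text alone is that disease follow-up does continue. Section 12.5.2 follows patients for PFS as well as survival. Table 3, footnote 5, expects completers at standard clinic visits two or three times a year, with blood drawn at progression, and Section 12.3 also plans blood at progression for completers. Clinical decline counts as progression without a scan. PFS is labelled descriptive, the Cox model is optional, and Section 9.3 disclaims power for the correlative features.

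Most of this stands, and it limits the size. It does not repair the rule: those sections require no MRI, footnote 5 and the blood draw in Section 12.3 do not cover patients who stop early without progression, and the stated censoring date makes no reference to an assessment.

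Four stronger readings are tempting and are not supported:
- **That median PFS will be roughly doubled.** This needs no progression at all to be detected after Day 140. The documents expect detection in completers, and lack of a protocol-scheduled MRI is not lack of imaging.
- **That most of the PFS period is unimaged.** Setting Day 140 against 36 months (1,096 − 140 = 956 days, 87%) uses a horizon the plan gives for survival only: "along with estimates for 12, 24, and 36-month survival".
- **That 12-month PFS is materially wrong.** The simulation in step 2 moves it by 2.7-8.6 percentage points, but the plan does not list 12-month PFS as a summary.
- **That the progression date is undefined.** The enhancing route needs an "increase in the sum of bi-perpendicular diameters of enhancing disease on two separate scans at least 4 weeks apart", and Section 15.6.5 does not say which scan dates the event. Section 12.6.3 defers to RANO 2.0, which may settle it and cannot be checked here.

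**Conclusion.** The concern holds as a minor point about the censoring date. Followed as written, Section 15.6.5 credits time without a disease assessment as progression-free. The resulting bias is upward, and it carries into median PFS, the Kaplan-Meier curves by CMV stratum, the optional Cox model and the Section 15.7.3 link.

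The size cannot be fixed from the documents. It is zero if all later progressions are detected. It averages about 2-52 days on the median if 10-30% of patients have no later MRI and no later documented progression, for true medians of 4-8 months. That share is assumed, and detection through clinical decline would lower it. The primary DLT endpoint and survival are unaffected.

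**What to change.** In Section 15.6.5, replace the PFS censoring sentence so that:
- a patient alive without documented progression is censored at the date of the last MRI-based RANO 2.0 assessment showing no progression, or at first vaccination if there is none;
- death, and progression declared on clinical decline, remain events whenever they occur;
- last patient follow-up is the censoring date for survival only.

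The date should be tied to an MRI. If a clinic visit without a scan qualified, much of the unscanned time would remain.

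The cost is the wording and one field for the date of the last disease assessment. No MRI, visit or patient is added. The downside is somewhat earlier censoring and wider PFS intervals. The change removes only part of the bias (0-35 of the 2-52 days in the simulation), because progressions that are never recorded stay missing under any rule.

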15.7 Exploratory Objectives

This study has four main exploratory objectives: (1) Assess the diversity of the P30-EPS-specific memory T cell repertoire via TCR sequencing, (2) Define the relationships between reported biomarkers of response to immunotherapy in GBM and survival, (3) Assess resected tumor for the expression of vaccine targets (i.e. EphA2, pp65, and survivin), and (4) Assess changes in the tumor immune microenvironment, mutational heterogeneity/clonality, neoantigen depletion, and their association with survival.

Additional objectives which are not explicitly stated here may also be explored. These additional analyses will be motivated by the results of analyses addressing the objectives stated a priori, as well as changes or new additional to the clinical literature.

15.7.1 Exploratory Objective: Diversity of the P30-EPS-specific memory T cell repertoire via TCR Sequencing

Objective: Assess the diversity of the P30-EPS-specific memory T cell repertoire via TCR sequencing

Analysis Set: Patients who have samples available for TCR analyses at baseline and after 5 P30-EPS vaccines

Outcome: Change in normalized entropy of P30-EPS-specific T cell clonotypes between baseline and post-vaccine 5

Hypothesis: P30-EPS vaccination will broaden the number of different T cell clones recognizing a single antigen

Analysis Plan: Patients' samples will be divided into two aliquots: one will be directly sequenced to record the overall repertoire; the other will be stimulated and expanded by the designated P30-EPS for 7 days and then sequenced. The raw sequencing reads from baseline (before vaccine #1) and an assessment after vaccine #5 will be stored in fastq files and pre-processed using the IMSEQ [67] software using reference barcode sequences from International Immunogenetics Information System [68]. TCR sequences are characterized by aligning the input to the reference V, D and J regions as well as the random regions. We will focus on the TCR beta-chain. To control alignment qualities, we will exclude reads with average quality score below 10. After the pre-processing step, the IMSEQ software will produce the clone-types of T cells. We will then derive the clonotypes and their relative frequencies. Clones which have fewer than 20 reads or 0.5% of total reads will be excluded. Alternatively, we will leverage a new method we developed to perform error-tolerance mapping. This method will not only produce the mapping results, but also assign a posterior probability to each read that measures how likely it belongs to a clone type.

With the P30-EPS-stimulated samples, we will perform Motif analysis to enrich P30-EPS-specific TCR clonotypes. All TCR clonotypes from the sequencing will be

included to generate all possible amino acid motifs with varying lengths using the R *tcR* package. Two separate pools of CDR3 sequences were created initially for each of these motifs from directly sequenced aliquot and P30-EPS-stimulated aliquot. To account for different sequence depths across samples, we will normalize the number of CDR3s containing each motif by the total number of CDR3s containing all motifs in each sample. The motif frequency ratios between directly sequenced aliquot and P30-EPS-stimulated aliquot will be compared. A higher ratio represents more abundant motifs in P30-EPS-stimulated aliquot compared with directly sequenced one, enabling the identification of a set of candidate motifs as P30-EPS-specific. The importance of each motif will be evaluated using both Mean Decrease Accuracy and Mean Decrease Gini in the random forest. A standard receiver operating characteristic (ROC) approach will be applied to evaluate the predictive power of each motif. These analyses will be performed using R *randomForest* [69] and *ROC* packages.

After the P30-EPS-specific CDR3 motifs are identified, we will map these motifs back to each individual TCR clones within the directly sequenced PBMC samples. These TCR clones will be considered to be P30-EPS-specific. For a given clone type, we will sum up all the read posterior probabilities if they exceed 0.2, and record the sum as the weighted frequency of the clone type. To test for overall clonal expansion, we will calculate the normalized entropy of the clonotypes at each time point. A decrease in entropy implies a decrease in diversity in clonotypes, and subsequently the expansion (increase in frequency) of one or more specific clonotypes. For each patient, the change in entropy over time will be computed. A Wilcoxon signed rank test will assess whether diversity has increased with vaccination.

15.7.2 Exploratory Objective: Define the relationship between reported biomarkers of response to immunotherapy in GBM and survival

Objective: Define the relationship between reported biomarkers of response to immunotherapy in GBM and survival

Analysis Set: Any available tumor tissue from patients on-study prior to and/or after immunotherapy with P30-EPS vaccine

Outcome: Association between the following: TMB, tumor-intrinsic Erk1/2 signaling, TMEM119+ (microglia) cell density, peripheral Ki67+ CD8 T cells, and gene expression signatures of MHC-class II, IFN- γ , and cell cycle/proliferation

Hypothesis: In patients with higher TMB, increased immune activation (Ki67+ CD8 T cells, MHC-class II, IFN- γ), and lower Erk1/2 signaling and microglial density, P30-EPS vaccination is more likely to enhance the antitumor immune response.

Analysis Plan: The following biomarkers that have been reported to be predictive for response to immunotherapy in GBM, will be assessed on surgically resected tumor

tissue using the noted approaches, including quantitative immunohistochemistry (qIHC), bulk RNAseq, and whole exome sequencing (WES):

- MEK-ERK activating mutations - WES; Zhao et al Nat Med 2019 [70]
- High frequency of p-ERK+ tumor cells - qIHC; Arrieta et al Nat Cancer 2021 [71]
- High MHC-class II gene expression - RNA-seq; Arrieta et al Nat Cancer 2021 [71]
- IFN γ signature; Cell cycle gene signature repression - RNAseq; Cloughesy et al Nat Med 2019 [72]
- Exhaustion signatures, inhibitory receptors - RNA-seq, qIHC; Lee et al. Nat Comm 2021 [73]
- Putative neoantigen depletion - WES, RNA-seq; Gromeier et al Nat Comm. 2021; preliminary data [74]

MEK-ERK activating mutations will be queried using existing WES data. qIHC will be performed for p-ERK1/2 and TMEM119 as described by Arrieta et al *Nature Cancer* 2021 [71].

To define T cell exhaustion/inhibitory receptors, we will also similarly quantify and define spatial PD-L1, CTLA4, PD1, TIGIT, and TIM3 expression in all tumor samples, using qIHC. Bulk RNA-seq data will be used to determine MHC-class II, IFN γ and cell cycle gene expression signatures, as well as differential expression of inhibitory receptors (TIGIT, TIM3, CTLA4, and PD1).

Neoantigen depletion will be predicted using the pVAC-seq pipeline. Briefly, for the pVAC-seq pipeline, neoantigens will be defined at 8-11-mer peptides from exonic nonsynonymous single nucleotide variants that bind to a patient's respective HLA class I molecule with a binding affinity score <500nM stronger than the wildtype peptide using NetMHCpan51. Neoantigen density will be expressed as ratio of observed to expected neoantigens. Expected neoantigen levels will be determined using a previously empirically derived rate of mutation that assumes no selection against neoantigen-causing mutations normalized to the silent mutation load for each patient's tumor [75]. MHC class I epitope predictors are imperfect in predicting actual MHC class I binding epitopes [76]. Thus, nonsynonymous mutation/TMB ratios will also be used to predict neoantigen depletion: lower non-synonymous mutations out of total mutations is surrogate measure of neoantigen density [77].

Each feature will be tested for its association with post- P30-EPS vaccine survival to determine if other biomarkers are superior in identifying P30-EPS vaccine responsive GBM patients. We will also test the relationships between each biomarker to determine if they identify the same patients, and to further define the nature of patients living longer after P30-EPS vaccination.

The associations between the various biomarkers will be explored with scattergrams, and correlation (Pearson or Spearman) with adjustment for multiple comparisons. For each biomarker, Receiver-operating curves will be performed to

assess the optimal threshold for differentiating short versus long-term survival; the sensitivity and specificity of each biomarker will be compared. A Cox proportional hazards model will assess the joint effect of all biomarkers on survival to discern if an integrated biomarker approach is more effective in predicting survival outcome. Correction for multiple comparisons using gene expression analyses will use the False Discovery Rate.

15.7.3 Exploratory Objective: Assess resected tumor for expression of the vaccine targets (i.e. EphA2, pp65, and survivin)

Objective: Assess resected tumor for expression of the vaccine targets (i.e. EphA2, pp65, and survivin)

Analysis Set: Any available tumor tissue from patients on-study prior to and/or after P30-EPS vaccination

Outcome: Association between the vaccine targets (EphA2, pp65, and survivin) and clinical outcomes

Hypothesis: Expression of vaccine targets will associate with survival and other exploratory endpoints

Analysis Plan: RNA-seq analysis of tumor tissue will be used to determine expression levels of vaccine targets, in transcripts per million and expression will be linked with survival and PFS after P30-EPS vaccination. For patients with available post-P30-EPS vaccination tumor tissue, pre- vs post P30-EPS vaccine expression levels of antigens will be determined to test if antigen escape/immunoediting of vaccine antigens occurs as well as if T cell inflammation post- P30-EPS vaccination associates with vaccine antigen expression.

15.7.4 Exploratory Objective: Assess changes in the tumor immune microenvironment, mutational heterogeneity/clonality, neoantigen depletion, and their association with survival.

Objective: Assess changes in the tumor immune microenvironment, mutational heterogeneity/clonality, neoantigen depletion, and their association with survival.

Analysis Set: Any available tumor tissue from patients on-study prior to and/or after P30-EPS vaccination

Outcome: Since productive immune surveillance is associated with immunoediting (e.g., depletion of immunogenic glioma cell clones), the associations between putative neoantigen depletion, mutational heterogeneity, gene expression signatures of T cell inflammation, and survival will be tested.

Hypothesis: Neoantigen depletion, reduced mutational heterogeneity, and increased T cell inflammation will be associated with improved survival in GBM patients treated with the P30-EPS vaccine.

Analysis Plan: The following assessments will be made if samples are available from patients who have baseline tumor tissue and tissue from a second surgical procedure after they have received the P30-EPS vaccine.

1. TMB suppression and putative neoantigen: will be determined to test if low TMB status in GBM is associated with TMB suppression and/or neoantigen depletion, or post-P30-EPS vaccination survival.
2. Gene expression signatures: T cell inflammatory/MHC class II gene expression signatures, and unbiased gene set enrichment analyses (Biocarta and Reactome), and long (overall survival >24 months) vs short (overall survival <24 months) survival will be performed to determine if patients with low TMB and/or longer survival after P30-EPS vaccine exhibit distinct gene expression signatures and/or changes in specific gene expression patterns in response to P30-EPS vaccine.
3. Mutational heterogeneity/clonality: will be predicted using subclonal deconvolution of WES for all samples using a pre-validated pipeline employing Mutect2 [78] for SNV and InDel calling, FACETS [79] for CNV calling, and PyClone-VI [80] for sub-clonal deconvolution. Cancer Cell Fractions (CCF) for each mutation within each sample will be determined and sample-mean CCFs will be tested for their relationship with post- P30-EPS vaccine survival and TMB.

To more comprehensively define the relationships between TMB and post- P30-EPS vaccine survival with the GBM tumor immune microenvironment and mutational clonality, single nuclei RNA sequencing (snRNAseq) may be performed for a subset of tumor samples. In addition, tumors from any patients surviving >24 months post-P30-EPS vaccine will also be analyzed, in order to ensure an informative comparison of post- P30-EPS vaccine survival with these features.

snRNAseq will be performed on snap frozen tissue to qualitatively define the tumor microenvironment and link tumor microenvironment features with vaccine antigen expression, mutational landscapes, and survival. snRNAseq will also be used to define exhaustion and immunosuppressive phenotypes of tumor-associated macrophages in post- P30-EPS vaccine tissue, as well as whether these cell type densities or states differ according to TMB or long vs. short survival.

These analyses are exploratory and will primarily leverage qualitative comparisons. Changes in TMB, neoantigen levels, cellular phenotypes, and mutation clonality will be qualitatively compared within patients and tested using paired t-tests. Comparisons of TMB/neoantigen depletion, gene expression, and clonality to TMB and post-P30-EPS vaccine survival will be performed using Spearman correlation, adjusted for multiple comparisons. Similarly, the change in each of these features will be correlated. SnRNAseq (tumor immune microenvironment) based analyses are largely intended to be qualitative assessments that will be tested for correlation with TMB and post- P30-EPS vaccine survival. Differential expression analysis

(DEseq2) for snRNAseq data will be adjusted for multiple comparisons using the False Discovery Rate.

